We have worked extensively with the Health & Social Care Information Centre (HSCIC), the organisation responsible for the design and maintenance of the Bowel Cancer Screening System (BCSS). The system is responsible for identifying the population eligible for screening in each of the five hubs and creating all the letters that are sent to the screening subjects and their GPs. For the purpose of our study the HSCIC modified the BCSS to enable selection of invitees registered with GP practices that endorse the BCSP prior to creation of each kit invitation letter (S9). In addition, the BCSS will be enabled to take into account the dates when GP-endorsed invitations need to be produced in any of the five hubs. The processes involved within the BCSS and the hubs are shown below in Figure 3.

The duration of this trial is 30 working days in each hub which will result in 15 clusters of invitees randomised to receiving an endorsed kit invitation letter and 15 control clusters in each hub. We plan that this intervention will take place in all hubs between Monday 1st Feb and Friday 11th March 2016.

Figure 3:

Comparators

Intervention 5 will provide data to compare the effectiveness of a GPE banner included on the S9 kit invitation letter against the usual S9 letter in the BCSP: it shall not involve any structural changes to the S9 letter.

Randomisation

Cluster randomisation will be used in this trial. Individuals who are routinely invited for screening in the NHS BCSP in England will be allocated to receive an intervention on randomly selected days within a pre-specified time-period. In consultation with all BCSP hubs we will identify trial dates which will enable us to run our intervention outside major public holidays or significant updates to the Bowel Cancer Screening System (BCSS). Prior to the start of the trial each of the BCSP hubs will receive a table with dates on which their population is due to receive GPE kit invitation letters (the intervention). These tables with randomisation dates will also be given to Health & Social (HSCIC), the organisation responsible for the BCSS.

Eligible population

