We will use IMD quintile here because of its demonstrated ability to explain area-level variation in bowel cancer screening uptake (2). IMD is freely available and widely accepted and used, enabling direct comparison of our results with other studies. IMD will be applied using the geographic unit of Lower Super Output Area (LSOA) level.

We have chosen to assess the proportion of FOB tests returned at 18 weeks from the pre-invitation to coincide with when the Bowel Cancer Screening System (BCSS) closes an episode due to non-response.

Secondary outcomes

- i) Time taken to return FOBt by IMD quintile
- ii) Proportion of spoilt kits by IMD quintile
- iii) Proportion of non-delivered kits by IMD quintile
- iv) Incremental cost per screening invitation
- v) Incremental cost per screening invitation, both by IMD quintile and overall
- vi) All of the above outcomes analysed using other socioeconomic (SE) variables

Statistics

Sample size

To calculate the required study size, we need to take into account:

- 1. The size of the effect/interaction we wish to detect.
- 2. The anticipated distribution of socioeconomic status and the expected participation by socioeconomic status in the control arm and by screening round.
- 3. The proportion of GPs agreeing to be included in the trial.
- 4. A variance inflation factor to account for the cluster (hub-day) randomisation.
- 5. The size of the effect/interaction by screening round.

In ASCEND, the combined effect of GP endorsement with introductory letter was a 3% overall increase in participation. As a failsafe, we design the trial using the more conservative 2% overall

estimate. We posit an interaction such that in the least deprived quintile, there is a 1% increase in participation with the intervention, in the second least deprived a 1.5% increase, and so on, with a 3% increase in the most deprived quintile.

The control group from the GP endorsement trial in ASCEND had the socioeconomic status distribution and completion rates by socioeconomic status shown in Table 1. Note that the percentages per quintile are not all 20% since socioeconomic status is associated with age and place of residence (in the latter case therefore being influenced by the proportions of subjects by hub). We anticipate these rates in the control group of the proposed trial and anticipate the intervention participation rates in the final column of Table 1.

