We calculated the required sample size using the method of Brentnall et al (2012). To obtain 90% power to detect the interaction as significant at 5% level with 2-sided testing, in an individually randomised study, we would require 11,714 individuals in each arm. In ASCEND, 80% of the GP's approached agreed to participate in the GP endorsement trial, giving 14,643(=11,714/0.8) subjects per trial arm. Also in ASCEND, we estimated a variance inflation factor for cluster randomisation of 1.7, but results post hoc suggest that a larger inflation would be more appropriate. We therefore use an inflation factor of 2.5, giving a total study size of 36,608 per arm, a total randomised of 73,216. Assuming approximately 3,000 kits are sent per hub-day, this indicates that we should randomise 25 hub-days. To cope with any plausible failures of our assumptions, we propose to randomise 100 hub-days to allow for subgroup analyses, completing trial accrual from the five hubs in four working weeks with a target population of 300,000.

In order to also consider subgroups by screening round, we propose a further increase to 150 hubdays. With 150 hub-days, we have a target population of 450,000. The smallest screening round subgroup in ASCEND1, prevalent screen first-time, comprised around 15% of the recruits. This would give 67,500 in this smallest subgroup. Within screening round subgroups, the variation between hub-days is around 20% lower than in the population as a whole, which in turn suggests a variance inflation factor of around 2. For 90% power for the same size of effect as expected overall, we would need 2 x 14,643 per arm, just under 30,000 per arm, 60,000 in total. Thus, the study size of 150 hubdays is likely to be more than adequate for subgroup comparisons. The trial will involve no additional costs or work on the part of hub staff if the trial size is increased as the GP endorsement and random allocation will be programmed within the Bowel Cancer Screening System.

Table 1. Expected socioeconomic status distribution, and intervention and			
control completion rates			
Socioeconomic	Percentage in	Control group	Anticipated
status (national	each quintile	completion	intervention
IMD quintile)	from ASCEND	percent by	group completion
		quintile from	percent
		ASCEND	
1 (least deprived)	23.5	66.0	67.0
2	23.5	62.6	64.1
3	21.1	58.0	60.0
4	17.3	51.5	54.0
5 (most deprived)	14.6	42.6	45.6

Data Analyses

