We will undertake a descriptive analysis of socio-demographic characteristics in the two arms across each intervention and analyse uptake differences by logistic regression (LR). Although randomisation should ensure comparability, the analysis will be performed with and without adjustment for age, sex, screening round and hub (4). The question of whether the intervention has a greater impact on uptake in the lower SE groups will be assessed by a test of interaction between trial arm and IMD quintile in the LR analysis. We will also use hierarchical LR to account for heterogeneities (i.e. due to varying policies and procedures in PCTs). We will adjust for incident episode versus prevalent episode status and check for heterogeneity of effects between incident and prevalent screens. The use of the maximum sample size from the calculation above will also enable subgroup analyses by sex, age, hub and incident versus prevalent screening round.

A secondary analysis of time taken to return the FOBt by IMD quintile will be examined using the log rank method (5). When comparing the intervention against usual practice, we will in the first instance compare all interventions to all controls on an intention-to-treat basis.

Finally, we will also examine effectiveness in terms of the SE variables identified in the ASCEND study.

Data Management

A Data Analyst working on behalf of all BCSP hubs has designed and piloted the data extraction algorithms. The raw data will be extracted by Health & Social Care Information Centre (HSCIC) from BCSS and pseudo-anonymised then given to the Data Analyst to clean. The postcode variable will be substituted with Index of Multiple Deprivation (IMD) score by HSCIC.

The Data Analyst has specified the data to be extracted by HSCIC and the National Office on behalf of the ASCEND2 research team. No patient identifiable information is required. Data transfer between HSCIC/the National Office and the Data Analyst will be via encrypted network connection (NHS.NET) and/or NHS Secure File Transfer (SFT).

The pseudo-anonymised raw data will be processed and further anonymised into the format required by the ASCEND2 academic statisticians. Any permutations of geo-demographic variables that could lead to potentially identifiable patient information will be subject to further levels of anonymisation.

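### Hub-days are randomised and the sample size is inflated for them, but the stated analysis names no hub-day term and gives PCTs as its only hierarchical level

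*Protocol*

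**What the plan says.** The Randomisation section states: "Cluster randomisation will be used in this trial". Whole days of invitations within a hub are allocated, and Study Design gives "15 clusters of invitees randomised to receiving an endorsed kit invitation letter and 15 control clusters in each hub". With five hubs that makes 150 clusters.

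The Sample size section lists among its requirements "A variance inflation factor to account for the cluster (hub-day) randomisation". It reports that ASCEND estimated this factor as 1.7, that post hoc results pointed higher, and then: "We therefore use an inflation factor of 2.5". Within screening-round subgroups it suggests a factor of around 2.

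Under Data Analyses the protocol will "analyse uptake differences by logistic regression (LR", fitted both unadjusted and adjusted for age, sex, screening round and hub. Whether the effect is larger in more deprived groups is tested as an arm by IMD quintile interaction in the same regression. The one multilevel element is additional: "We will also use hierarchical LR to account for heterogeneities (i.e. due to varying policies and procedures in PCTs". For the secondary outcome: "A secondary analysis of time taken to return the FOBt by IMD quintile will be examined using the log rank method". The word hub-day does not appear in that section, and no other device for handling the randomised cluster is given.

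**The concern.** In a cluster-randomised comparison the variance of the arm effect must include variation between the randomised units. Here those units are hub-days, and the protocol itself treats their variation as large enough to multiply the sample size by 2.5. None of the terms named in the analysis represents it. A hub covariate removes differences between the five hubs but not day-to-day variation within a hub. A PCT level represents variation between primary care trusts, not between the days that were allocated.

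If the section is followed literally, intervals for overall uptake are too narrow and false claims of increased uptake become too frequent. Raising uptake is a stated aim, and a positive result could change letters across a national programme. The increase to 150 hub-days does not repair this: inflation depends on cluster size and intracluster correlation, so more clusters add power but leave the size of a test that ignores clustering unchanged.

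**Working it through.** **1. The protocol's inflation chain (Sample size).**
- 11,714 / 0.8 = 14,642.5, stated as 14,643 per arm.
- 14,643 × 2.5 = 36,607.5, stated as 36,608 per arm.
- 2 × 36,608 = 73,216; 73,216 / 3,000 = 24.4, stated as 25 hub-days.

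The chain reproduces. The factor of 2.5 is applied to a sample size stated for the interaction test (two-sided 5%, 90% power).

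**2. What 2.5 implies.** The sample size section sets the cluster size: "Assuming approximately 3,000 kits are sent per hub-day". With V = 1 + (m − 1) × ICC and m = 3,000, ICC = 1.5 / 2,999 = 0.0005. A very small correlation is enough, because the clusters are large.

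**3. Size of a test that ignores V.** If the true variance is V times the one used, a nominal two-sided 5% test has size 2 × (1 − Φ(1.96/√V)). The same 5% two-sided level is assumed for overall uptake.

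| V | Source in protocol | 1.96/√V | True size | Coverage of nominal 95% interval |
|---|---|---|---|---|
| 1.7 | ASCEND estimate | 1.503 | 13.3% | 86.7% |
| 2.0 | within screening round | 1.386 | 16.6% | 83.4% |
| 2.5 | planning value | 1.240 | 21.5% | 78.5% |

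At V = 2.5 the interval should be √2.5 = 1.58 times wider.

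**4. Does this carry over to the interaction?** A hub-day can contain all IMD quintiles, so the interaction is largely a contrast within hub-days, and a shift common to all quintiles on a given day mostly cancels. This was checked by simulating 150 hub-days of 3,000 with the Table 1 quintile shares and control rates, no treatment effect, and 20,000 runs. Each run was analysed on the log-odds scale with variances that ignore hub-day, and the interaction was taken as a linear trend over quintiles.

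- *Hub-days differ only in level.* The hub-day standard deviation was √(1.5 / (3,000 × 0.24)) = 0.0456 on the log-odds scale, or about 0.0456 × 0.24 = 1.1 percentage points of uptake. Rejection: arm effect 21.7%, interaction 5.3%.
- *The IMD slope also varies, enough to give V = 2.5 for the trend.* Rejection: arm effect 21.7%, interaction 21.5%.

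A separate beta-binomial simulation of overall uptake, with 75 against 75 hub-days of 2,400 (3,000 × 0.8), rejected in 21.6%.

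The formula and simulations agree for overall uptake. For the interaction the answer depends on how much the IMD slope varies between hub-days, for which the protocol gives no figure.

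**The case against.** Three objections deserve weight.

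*The variance estimator is normally left to the SAP.* Logistic regression names a model, not an assumption of independent errors; with cluster-robust errors or a random intercept it is still logistic regression. A reader might infer that the protocol commits to an ordinary, independence-based analysis. It does not say so, and the same holds for the log-rank sentence. What defeats this as a full answer is that the protocol is not merely silent. It lists covariates down to hub, introduces a hierarchical model, and gives that model a level which is not the randomised one. A SAP faithful to that text would cluster on the wrong unit.

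*The inflation may be smaller in the adjusted analysis.* Allocation is balanced 15 to 15 within each hub, and hub and screening round are covariates. If part of the 2.5 is between-hub or round-mix variation, the remaining factor is lower. This stands. It means 21.5% is the top of a range, and the true size could fall below 13% if adjustment takes V under 1.7.

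*The primary question is the interaction.* A reader might infer that the trial's 5% test runs at about 21%. That is not supported as a flat statement. The interaction can be close to nominal, and the protocol's use of 2.5 for it may be planning caution, not a measured inflation of that test.

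Two further inferences are also unsupported: that PCTs are crossed with hub-days, and that the hub-day identifier will be lost from the extract. The protocol states neither; the further anonymisation it describes concerns geo-demographic combinations.

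**Conclusion.** The point holds as a mismatch within the protocol between the unit it randomises and sizes for, and the levels its analysis names. The size of the consequence is conditional.

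- *Overall uptake:* a true size of about 13% to 21.5% for a nominal 5% test if hub-day is left out and the effective inflation is between 1.7 and 2.5; less if hub and screening-round adjustment absorbs some of it.
- *Arm by IMD interaction:* between about 5% and about 21.5%, depending on slope variation between hub-days. The upper end applies if the protocol's factor of 2.5 is right for this test.
- *Time to return:* the same omission applies to the log-rank comparison of arms. Its size was not calculated.

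These figures assume that the analysis is carried out as written, with no hub-day term added elsewhere.

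**What to change.** In Data Analyses, name hub-day as the cluster in the primary logistic regression, for both overall uptake and the arm by IMD interaction. Either hub-day cluster-robust or GEE standard errors, or a hub-day random intercept with a random IMD slope for the interaction, would do. A random intercept alone would not cover slope variation in the interaction. Keep hub as a fixed stratum. In the hierarchical regression sentence, make hub-day the required level and retain PCT only as an additional or sensitivity level. For time to return, use a variance clustered on hub-day, for example a cluster-adjusted log-rank test or a Cox model with hub-day-robust errors.

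The cost is protocol wording, minor analysis work and wider confidence intervals. The allocation and the number of hub-days need not change for this.

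### The stated adjustment set for the uptake regression omits IMD quintile, giving up a little precision in the overall and subgroup arm comparisons

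*Protocol*

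**What the plan says.** The Data Analyses section of the protocol compares uptake between arms by logistic regression and fixes the covariates: "the analysis will be performed with and without adjustment for age, sex, screening round and hub (4"). It adds adjustment for incident or prevalent episode status and a multilevel model: "We will also use hierarchical LR to account for heterogeneities (i.e. due to varying policies and procedures in PCTs"). IMD has one stated role in these models. The question of a larger effect in more deprived groups is to be "assessed by a test of interaction between trial arm and IMD quintile in the LR analysis".

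Elsewhere the protocol treats IMD as a strong predictor. Under Primary Outcome it is chosen "because of its demonstrated ability to explain area-level variation in bowel cancer screening uptake (2"). Table 1 runs from "1 (least deprived) 23.5 66.0 67.0" to "5 (most deprived) 14.6 42.6 45.6" (share of invitees, control %, anticipated intervention %). Data Management says that postcode will be replaced by an IMD score. Higher uptake is the first part of the aim under Aims and Objectives.

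**The concern.** Whole hub-days are randomised, 15 intervention and 15 control days in each of five hubs (Study Design). If the invitees on intervention days happen to be somewhat more or less deprived than those on control days in the same hub, that difference passes into the overall arm comparison. IMD is fixed before allocation, and it is the only predictor for which the protocol gives uptake rates. Leaving it out therefore gives away precision that could be had at no cost.

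The same list would naturally serve the incident/prevalent heterogeneity check and the subgroup analyses by sex, age and hub. A single-hub analysis has only 15 days per arm over which the mix can average out. The protocol also plans a descriptive comparison of socio-demographic characteristics by arm. If that showed a deprivation imbalance, adding IMD at that stage would be a post hoc choice.

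**Working it through.** **Inputs.** Quintile shares and rates: Table 1. Inflation factor 2.5 and about 3,000 kits per hub-day: Sample size. Endorsing practices 80%: Exclusion criteria and Sample size. Hub-days: 5 × 15 = 75 per arm. Between-day SD of IMD mix: not given, so assumed.

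**The plan's own figures.** 11,714 / 0.8 = 14,642.5, stated as 14,643. 14,643 × 2.5 = 36,607.5, stated as 36,608. Twice that is 73,216, and 73,216 / 3,000 = 24.4, stated as 25 hub-days. This chain reproduces. The starting 11,714 is a sample size for the interaction ("To obtain 90% power to detect the interaction as significant at 5% level with 2-sided testing"). It did not reproduce from Table 1 (trend-interaction calculations gave about 106,000 to 139,000 per arm), but the cited method paper is not at hand. That is a separate matter, and nothing below uses 11,714.

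**Overall rates.** Weighting Table 1 by its shares gives control 57.59%, intervention 59.47%, difference 1.88 points. The text says "we design the trial using the more conservative 2% overall" estimate; 1.88 is what the table implies.

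**How much IMD explains in individuals.**
- Between-quintile variance: Σ share × (rate − 0.5759)² = 0.00166 + 0.00059 + 0.00000 + 0.00064 + 0.00328 = 0.00618 before rounding of the terms.
- Total binary variance: 0.5759 × 0.4241 = 0.2442.
- Share: 0.00618 / 0.2442 = 2.5%.

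**Individual-level gain** (logistic Wald test of arm, 90% power, two-sided 5%). n per arm = (1.960 + 1.282)² × V / b² = 10.507 × V / b², where b is the log odds ratio and V is its variance × n per arm.
- Without IMD: b = 0.07746, V = 8.243, n ≈ 14,434.
- With IMD as a factor: b = 0.07931, V = 8.440, n ≈ 14,098.
- Gain: 336 / 14,434 = 2.3%. The odds ratio moves from 1.081 to 1.083.

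**Variance of the overall effect as planned.**
- Endorsing-practice invitees per hub-day: 3,000 × 0.8 = 2,400, so 75 × 2,400 = 180,000 per arm.
- SE = √(2.5 × 2 × 0.2442 / 180,000) = 0.260 points.
- ICC = 1.5 / 2,399 = 0.000625, so the between-hub-day SD is √(0.000625 × 0.2442) = 1.24 points.

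**Cluster-level gain.** Let s be the SD, between days within a hub, of expected uptake due to IMD mix. Its contribution to the SE of the arm difference is s × √(2/75).

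| Assumed s (points) | Contribution to SE | 95% chance range | Share of variance (÷ 0.260²) | SE with that part removed |
|---|---|---|---|---|
| 0.2 | 0.033 | ±0.06 | 2% | 0.258 |
| 0.5 | 0.082 | ±0.16 | 10% | 0.247 |

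To give s a scale: moving 1% of a day's invitees from quintile 1 to quintile 5 changes expected uptake by 0.01 × (66.0 − 42.6) = 0.234 points. So s = 0.2 to 0.5 corresponds to swaps of about 0.9% to 2.1% of invitees. Ordinary sampling of 2,400 people gives √(0.00618 / 2,400) = 0.16 points. That is part of the binomial variance and adds about 1% (2.5% / 2.5) to the shares above.

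With 3,000 per hub-day instead of 2,400, the SE is 0.233 points and the shares are 2% and 12%.

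**One hub alone** (15 v 15 days, 36,000 per arm). SE = √(2.5 × 2 × 0.2442 / 36,000) = 0.58 points. The chance range from IMD mix is 1.96 × s × √(2/15), which is ±0.14 points at s = 0.2 and ±0.36 at s = 0.5.

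**The case against.** The strongest reply is that this leaves the primary question untouched. The primary outcome is uptake in each IMD quintile, tested by the arm-by-IMD interaction, and that model needs the IMD main effect. Overall uptake is in the aim but in neither the primary nor the secondary outcome list. One could also read age, sex, round and hub as terms added to a regression that already holds arm and IMD. The first two points stand and confine the concern to the overall and subgroup comparisons. The last is a possible reading, but the protocol names its covariates and does not say so.

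A reader might infer that the overall comparison is biased. It is not. Days are allocated at random, and chance differences in deprivation mix are part of ordinary sampling error, already inside the inflation factor. Allocation of 15 v 15 within hub together with hub adjustment removes between-hub differences in deprivation, and the PCT-level model may absorb some local ones. Only the within-hub, day-to-day part clearly remains.

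A reader might also infer a large loss. At s = 0.8 points the share of the overall variance would be 25%, but nothing in the protocol supports day-to-day swings of that size within a hub. Nor is power at risk: 1.88 / 0.260 gives z of about 7.2, and removing the IMD part at s = 0.5 raises it only to about 7.6. The protocol itself expects 150 hub-days to be ample for subgroups.

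Finally, IMD cannot be called the strongest predictor overall, because no rates are given for age, sex or round. Nor can it be assumed complete on every record: the protocol states only the replacement of postcode, and it foresees further anonymisation of some geo-demographic combinations.

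**Conclusion.** The point holds as a minor one. The protocol lists its adjustment covariates and leaves out the one variable whose relation to uptake it documents in figures. The cost is some precision, and unadjusted chance imbalance in within-hub deprivation mix, in the overall, incident/prevalent and subgroup comparisons of uptake. Validity and the primary interaction test are not affected.

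Only the individual-level gain of about 2.3% in sample size follows from the protocol's own figures. The 2% to 10% of the overall variance rests on the assumed between-day SD of 0.2 to 0.5 points, on 2,400 invitees per hub-day and on the inflation factor of 2.5. The protocol does not allow that SD to be pinned down.

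**What to change.** In Data Analyses, change the adjustment set to age, sex, screening round, hub and IMD quintile for the overall uptake comparison, the incident/prevalent heterogeneity check and the sex, age and hub subgroup models. Keep the unadjusted analysis alongside, as already planned. State that the adjusted odds ratio is then conditional on IMD; on Table 1 it shifts from about 1.081 to 1.083.

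The cost is a change of wording. The IMD score is already to be supplied with the data, and no extra data collection, recruitment or change to randomisation is needed.
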